6.3 Dose Adjustments

Dose adjustments for both DFP and DFX will be allowed for efficacy reasons (scaling up) or for safety reasons including the presence of markers indicative of over-chelation (scaling down).

DFP can be scaled up in steps of 12.5 mg/kg/day (to a maximum daily dose of 100 mg/kg) according to the individual patient's response defined as an increase of serum ferritin levels > 20% compared to the previous determination.

DFX will be scaled up in steps of 5 to 10 mg/kg (to a maximum daily dose of 40 mg/kg) according to the individual patient's response defined as an increase of ferritin levels > 20% compared to the previous determination.

For patients with a stable serum ferritin value >1500 (no increase or any increase <20%) and not showing a downtrend over a 3-month-period , DFP or DFX can be also increased.

DFP and DFX must be scaled down for the safety reasons detailed in **Table 4**.

Table 4. Scale down adjustment for DFP and DFX (safety reasons)

Serum creatinine increased by >33% from baseline OR Reduction in creatinine clearance (estimated with the Schwartz formula) ≤ 90ml/min and >60 ml/min in two consecutive measurements	No dose adjustment.	Reduce DFX in steps of 10 mg/kg/day until value returns to baseline value and continue DFX with the adjusted dose for 1 month. If the increase persists interrupt DFX. If after DFX interruption value returns to baseline value or > 90 ml/min for creatinine clearance restart DFX at 50% of the last dose and then escalate by 10 mg/kg/day at 1 month intervals provided that value increase does not recur. Monitor serum creatinine, creatinine clearance and urine protein/creatinine ratio weekly (+/- 7 days) during the period of abnormal value and during the first month after dose modification, then monthly.
Urine protein/creatinine ratio ≥ 0.5 in two consecutive measurements	No dose adjustment.	Reduce DFX in steps of 10 mg/kg/day until value returns to < 0.5. If the increase persists interrupt DFX. After the ratio improves, restart DFX at 50% of the last dose and then escalate by 10 mg/kg/day at 1 month intervals provided that value increase does not recur. Monitor serum creatinine, creatinine clearance and urine protein/creatinine ratio weekly (+/- 7 days) during the period of abnormal value and during the first month after dose modification, then monthly.
ALT or AST > 10 ULN	Interrupt DFP. When levels return to < 5 ULN, restart DFP at 50% of the last dose and after 1 month scale it back up to the former dose.	Interrupt DFX. When levels return to < 5 ULN, restart DFX at 50% of the last dose and then escalate by 10 mg/kg/day at 1 month intervals provided that value increase does not recur.

CONFIDENTIAL

Severe skin rash	No dose adjustment.	Interrupt DFX . Once resolved, restart DFX at 50% of the last dose and then escalate by 5 mg/kg/day at two-weeks intervals.
Ferritin \leq 500 ng/ml	Reduce DFP to 50% of last dose. If ferritin is still <500 ng/ml at subsequent monthly evaluation, DFP may continue having consulted the Coordinating Investigator. When value returns > 500 ng/ml DFP can be scaled up to full dose.	Reduce DFX to 50% of last dose. If ferritin is still <500 ng/ml at subsequent monthly evaluation, DFX may continue having consulted the Coordinating Investigator. When value returns > 500 ng/ml restart DFX at 50% of the last dose and then escalate by 10 mg/kg/day at 1 month intervals.
Neutropenia(neutrophil count $<1500/\text{mm}^3$ and $\geq 1000/\text{mm}^3$ in two consecutive measurements)*	Interrupt DFP and monitor neutrophil count every 1-3 days or more frequently. When value returns $> 1500/\text{mm}^3$ for two consecutive measurements, and if deemed safe by the investigator, restart DFP at the last dose after having consulted the Coordinating Investigator.	Interrupt DFX and monitor neutrophil count every 1-3 days or more frequently. When value returns $> 1500/\text{mm}^3$ for two consecutive measurements, and if deemed safe by the investigator, restart DFX at the last dose after having consulted the Coordinating Investigator.
Moderate Neutropenia (neutrophil count $<1000/\text{mm}^3$ and $> 500/\text{mm}^3$) OR Severe Neutropenia/Agranulocytosis (neutrophil count $< 500/\text{mm}^3$) Infection	Interrupt DFP. Exit from the protocol.	Interrupt DFX. Exit from the protocol.
Arthralgia	Interrupt DFP until neutrophil count is checked. If neutrophil count is $> 1500/\text{mm}^3$, two consecutive measurements, and if deemed safe by the investigator, restart DFP at the last dose after having consulted the Coordinating Investigator. If symptoms persist after appropriate treatment, reduce DFP to 50% of last dose until resolution and then scale it back up to the former dose.	Interrupt DFX until neutrophil count is checked. If neutrophil count is $> 1500/\text{mm}^3$, two consecutive measurements, and if deemed safe by the investigator, restart DFX at the last dose after having consulted the Coordinating Investigator. If symptoms persist after appropriate treatment, reduce DFX by 50% until resolution and then escalate by 10 mg/kg/day at 1 month intervals to the former dose.
Nausea/ Abdominal Pain/	If symptoms persist after appropriate treatment, reduce DFX	If symptoms persist after appropriate treatment, reduce DFX

Vomiting	DFP to 50 mg/kg/day until resolution and then scale it back up to the former dose.

* For details on clinical management of all neutropenia, please refer to Section 7.3.18 "Neutrophil count and Neutropenia management" and Section 16.6 "Instructions for rapid notification of Neutropenia".
	

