Deferasirox (DFX, Exjade®) the second approved oral chelator, is a once-daily orally active iron chelator, firstly introduced in USA, and authorised in Europe under the Centralised Procedure for treating chronic iron overload due to frequent blood transfusions (≥ 7 ml/kg/month of packed red blood cells) in patients with beta thalassaemia major above 6 years of age and in patients under 6 years of age when DFO therapy is contraindicated. The safety and efficacy profile of DFX was compared with DFO, and non-inferiority to this drug was demonstrated in patients with LIC ≥ 7 mg Fe/g dw. Post marketing long-term data have identified renal impairment as a safety risk associated with DFX therapy in both paediatric and adult patients and consequently the SmPC has been updated accordingly (Annex 1). Nevertheless, DFX with its PK profile allowing the maintenance of plasma levels within the therapeutic range for 24-hour period, and permitting once-daily oral administration, is currently the most widely used chelator in the paediatric subset (Ceci A et al., 2011).

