The target patient population consists of 388 outpatients affected by hereditary haemoglobinopathies requiring chronic transfusion and chelation, randomized 1:1 in two groups of 194 patients each to ensure 310 evaluable patients. Chelation naïve and not naïve patients aged from 1 month to less than 18 years will be recruited. A staggered approach will be applied to patients aged less than 6 years (10% of the total sample), which will be recruited after results from the PK Study (Study DEEP-1, EudraCT n. 2012-000658-67) will be available.

Experimental arm: patients administered with DFP at 75-100 mg/kg/day for seven days per week. In patients aged less than 6 years the dose will be defined according to the results of the PK Study (Study DEEP-1, EudraCT n. 2012-000658-67). DFP daily dose will not exceed 100 mg/kg.

Control arm: patients administered with DFX at 20-40 mg/kg/day as recommended by the currently approved European SmPC (last update 10/08/2011). DFX daily dose will not exceed 40 mg/kg.

Details on the starting dose and subsequent dose adjustments are reported in **Section 6**.

The **treatment duration** for both groups is 12 months.

4.1Non-inferiority margin

This study is designed to demonstrate the **non-inferiority** of a new liquid DFP (80 mg/mL) formulation in comparison with DFX in terms of percentage of successfully chelated patients as described in **Section 4.3**.

DFP will be declared non inferior to DFX if the lower limit of the 95% confidence interval for the difference in the proportion of successful chelation in the two groups is above -12.5%. The choice of this margin is based on clinical considerations starting from the available evidences for the effects of DFX at both ferritin and cardiac levels. For details please refer to **Section 11**.

4.2Choice of comparator

DFP will be compared to the oral chelating agent DFX. The rationale for comparing two oral chelators derives from the recent literature data reporting that oral chelating agents currently represent the most widespread adopted therapy in the paediatric age, due to good compliance, improved QoL and reduced burden of the disease (Ceci A et al, 2011).

4.3Primary endpoint

The primary endpoint will be the measure of treatment efficacy defined as the percentage of patients successfully chelated, as assessed by serum ferritin levels (in all patients) and cardiac MRI T2* (in patients above 10 years of age able to have an MRI scan without sedation).

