6.2 Deferasirox

Patients will be enrolled in the control arm at a DFX starting dose which depends on patient current therapy at screening as summarised in **Table 3**.

Table 3. Starting dose for DFX arm

None (Naïve patient)	20 mg/kg body weight
Deferiprone	20 mg/kg body weight
Deferoxamine	Half DFO dose (but not less than 20 mg/kg body weight)
Deferasirox	Current patient's posology (but not higher than 40 mg/kg)

For all naïve patients and patients on DFP at screening the starting DFX dose will be 20 mg/kg body weight. If the patient's chelation therapy at screening is DFO, the starting dose of DFX will be numerically half that of the DFO dose (e.g. a patient receiving 40 mg/kg/day of DFO for 5 days per week (or equivalent) could be transferred to a starting dose of 20 mg/kg/day of DFX) but, in any case, to a starting dose not inferior to 20 mg/kg/day.

If the patient's chelation therapy at screening is DFX, the patient starting dose of DFX will be his/her current posology as long as this does not exceed 40 mg/kg.

An initial dose of 30 mg/kg will be allowed for patients who require reduction of elevated body iron levels (defined as serum ferritin level > 2500 ng/ml or MRI T2* < 20 ms).

DFX tablets will be available at dosage strengths of 125 mg, 250 mg and 500 mg DFX, in re-labelled commercial packs containing dispersible tablets in PVC/PE/PVDC/Aluminium blisters.

The individual daily doses of DFX and the tablets composition contributing to the daily dose will be calculated by the investigator based on the patient's body weight through the following formula:

Total daily dose (mg) = dose level (mg/kg/day) × body weight (kg)

Doses must be rounded to the nearest whole tablet size as recommended in the Exjade® SmPC (**Annex 1**).

DFX must be taken once a day on an empty stomach at least 30 minutes before food, preferably at the same time each day. The tablets can be dispersed by stirring in a glass of water or orange or apple juice (100 to 200 mL) until a fine suspension is obtained. Dispersion in carbonated drinks or milk is not recommended.

After the suspension has been swallowed, any residue must be re-suspended in a small volume of water or juice and swallowed. The tablets must not be chewed or swallowed whole.

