9. INTERRUPTION OF TREATMENT

This section deals with a patient's premature withdrawal from the study before completing all scheduled visits. An individual subject may be withdrawn at the discretion of the responsible investigator and the study team for the reasons listed hereby. In the event one or more subjects are withdrawn, additional subjects may be enrolled to ensure an adequate number of subjects complete the cohort.

Reasons that a patient must discontinue participation in a clinical study are considered to constitute one of the following:

1. unsatisfactory therapeutic effect (quarterly increase in ferritin levels of at least 1500 ng/ml as detected by two determinations performed at no more than two weeks interval, or if cardiac MRI T2* decreases under 10ms)
2. subject's condition no longer requires study treatment
3. DFX treatment at 10 mg/kg/day (for safety reasons) for more than 4 weeks
4. DFP or DFX administration suspended (for safety reasons) for more than 4 weeks
5. adverse event(s) requiring change of chelation therapy, including moderate or severe Neutropenia
6. significant protocol violation
7. subject/legal guardian withdrew consent/assent
8. lost to follow-up
9. administrative problems
10. death

In the absence of a medical contraindication or significant protocol violation, the investigator may make an effort to keep the subject in the study. Should a subject withdraw or be withdrawn by the legal guardian, he/she has to complete a full set of the 'end-of-study phase assessments', i.e. a full V16 evaluation. Relevant records will have to be done on the corresponding CRF pages.

This requirement does not refer to patients who passed the screening and washout period and were found not to be eligible for treatment.

Patients prematurely withdrawn from the treatment will be considered treatment failures.

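### Table 4's DFX clearance trigger stops at 60 ml/min, and no visible rule states an action at or below that level

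*Combined protocol and SAP*

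**What the plan says.** Section 6.3 makes the Table 4 reductions mandatory. The renal row has two limbs: "Serum creatinine increased by >33% from baseline OR Reduction in creatinine clearance", the latter estimated by the Schwartz formula and limited to "≤ 90ml/min and >60 ml/min in two consecutive measurements". For DFX, the action is to step down by 10 mg/kg/day until the value is back at baseline, then "continue DFX with the adjusted dose for 1 month". DFX is interrupted if the abnormality persists, and weekly monitoring of creatinine, clearance and urine protein applies. Deferiprone (DFP) has no dose adjustment in this row.

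The next visible row concerns urine protein. Nothing visible in Table 4 addresses clearance at 60 ml/min or below.

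Section 5.2 excludes patients with serum creatinine above the upper limit for age, and patients with a known contraindication to DFX. It states no clearance floor. Section 9 lists the withdrawal reasons and gives no clearance level.

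Section 7.3.16 has creatinine and clearance measured at every visit from V1 to V15, and weekly in the first month after starting or changing therapy. Section 3.1 names renal impairment as an identified DFX risk and refers to the label in Annex 1.

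**The concern.** A safety trigger should not switch off as the value gets worse. Read literally, the clearance limb applies at 62 ml/min and stops applying at 58. The neutropenia rows of the same table do this properly: a mild band is followed by a lower tier with a stronger action, exit from the protocol. The renal band has no such tier.

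At stake is whether a child on DFX with a confirmed fall to 60 ml/min or below gets the mandatory dose reduction and weekly monitoring. If neither limb is met, any action depends on the investigator's judgement and not on the written rule.

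**Working it through.** There is no figure in the plan to reproduce here. The check is whether the creatinine limb catches what the clearance limb leaves out.

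**Inputs**
- Creatinine limb: rise above 33% from baseline (Table 4).
- Clearance limb: above 60 and up to 90 ml/min, on two consecutive measurements (Table 4).
- Clearance by the Schwartz formula (Section 7.3.16). Assumed form: clearance = k × height / creatinine, with k fixed.

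**Formula.** With no growth, creatinine ratio = baseline clearance / current clearance. The creatinine limb fires only if this exceeds 1.33. So the highest baseline it misses is 1.33 × current clearance, and the lowest clearance reachable without firing it is baseline / 1.33.

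**Highest baseline missed, by repeated value**

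| Repeated clearance (ml/min) | Calculation | Highest baseline missed (ml/min) |
|---|---|---|
| 60 | 60 × 1.33 | 79.8 |
| 58 | 58 × 1.33 | 77.1 |
| 55 | 55 × 1.33 | 73.2 |
| 50 | 50 × 1.33 | 66.5 |

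Growth lowers these edges. If height rises by 6% over the year (an assumption), the edge for 60 is 79.8 / 1.06 = 75.3, and for 58 it is 77.14 / 1.06 = 72.8.

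**Worked path.** Baseline 75, then 62, then 58 repeatedly:
- At 62: 75 / 62 = 1.21, a 21% creatinine rise. The reading is in the band, but there is only one below baseline.
- At 58: 75 / 58 = 1.293, a 29.3% rise. This is below 33%, and 58 is outside the band.
- If the limb means a fall from baseline, neither limb is met. A second 62 in place of the first 58 would have met the clearance limb.

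**Low entrant.** A patient entering at 60 is never in the band while at or below that value. The creatinine limb does not fire until clearance drops below 60 / 1.33 = 45.1.

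**Covered cases.** Higher baselines are caught by the creatinine limb: 80 to 58 is a 37.9% rise, and 90 to 60 is 50%.

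**The case against.** The strongest objection is that few patients would slip through. A patient starting between 61 and about 77 must get to 60 or below without ever having two consecutive readings below baseline and still above 60. With weekly and then monthly measurement, a gradual decline will usually give such a pair. In a simulated fall from 75 to 57 over 3 to 6 months, with an assumed measurement CV of 5 to 10%, neither limb fired in only about 2 to 8% of patients. The patient must also have entered with creatinine within the limit for age and must not trigger the proteinuria row. This stands, and it limits the size of the problem. It does not help the patient who enters at or near 60, or one who falls quickly.

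Second, Annex 1 may already hold an entry or stop level. Section 4 has DFX dosed "as recommended by the currently approved European SmPC", and a contraindication to DFX is an exclusion. This also stands, so the annex should be read first. Still, the operative table is Table 4, and it neither states such a level nor refers to one in this row.

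Third, Section 7.3.2 leaves the clinician free to change treatment, Section 9 allows withdrawal for adverse events, and the DSMC receives safety updates twice a year. These are real safeguards, but none supplies a trigger at 60 or below.

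A reader might go further and infer a bias in the efficacy result. The argument would be that the band is an absolute range, so unchanged entry values of 61 to 90 fire the row. A patient starting at 20 mg/kg then drops to 10 mg/kg for a month and meets the withdrawal reason "DFX treatment at 10 mg/kg/day (for safety reasons) for more than 4 weeks". Because "Patients prematurely withdrawn from the treatment will be considered treatment failures", failures would accrue only on DFX. The documents do not support this. The limb speaks of a reduction, and the action ends on return to baseline. An unchanged value is not a reduction and already meets that end point. The documents also give no clearance distribution from which to size an effect, and the primary analysis is on the per-protocol population PP1 (Section 11.6), with ITT as corroboration.

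**Conclusion.** The point holds as a gap in a mandatory safety rule. At 60 ml/min or below the clearance limb no longer applies, and no visible rule replaces it. The creatinine limb leaves uncovered a repeated 60 from a baseline of about 80 or below, a repeated 58 from about 77 or below, and any fall from 60 down to about 45. The first two apply only where two consecutive in-band readings have not already fired the row.

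These figures assume the standard Schwartz proportionality and no growth; growth narrows the range. The number of patients affected cannot be estimated from the documents and is probably small. Nor do the documents show that the trial lacks a renal stop level altogether, because Annex 1 could not be read. The change is worth making because the rule protects children from a named risk of the comparator and the correction is cheap. Confidence is medium.

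**What to change.** Read Annex 1 first, then amend the renal row and the entry criteria:

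1. **Remove the lower bound.** The clearance limb becomes: reduction from the patient's baseline to ≤90 ml/min in two consecutive measurements, with values ≤60 counting.
2. **Add a lower tier.** Two consecutive values ≤60 ml/min lead to DFX interruption, or at least to the existing reduction and weekly monitoring. Restart only when clearance is back above 60 ml/min. Align the level with any stop level in Annex 1.
3. **Apply the same level at entry.** Use the V1 clearance, so that stable low entrants are dealt with at screening. Otherwise they meet a tier whose existing end point, return to baseline, they already satisfy.

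Keeping the lower bound and only adding the words *from baseline* would not do, because it leaves the gap in place.

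The cost is a wording amendment to one table row and one entry criterion, using measurements already scheduled. A few DFX patients may be reduced, interrupted or excluded earlier. Anyone suspended for safety for more than 4 weeks would be withdrawn under Section 9 and counted as a failure, so the level should be settled on clinical grounds before it is written in.

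### Table 4, ferritin ≤500 row: the deferasirox (DFX) recovery instruction says to restart a drug that was never stopped and leaves the dose undefined; a narrow clash with Section 9 follows from the same row

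*Combined protocol and SAP*

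**What the plan says.** Section 6.3 makes the reductions in Table 4 mandatory: "DFP and DFX must be scaled down for the safety reasons detailed in" that table. Ferritin at or below 500 ng/ml is one of its rows.

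In that row both drugs are first cut to half. For DFX the cell then adds: "If ferritin is still <500 ng/ml at subsequent monthly evaluation, DFX may continue having consulted the Coordinating Investigator". On recovery it says: "When value returns > 500 ng/ml restart DFX at 50% of the last dose and then escalate by 10 mg/kg/day at 1 month intervals". The DFP cell of the same row ends differently: "When value returns > 500 ng/ml DFP can be scaled up to full dose".

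The DFX cell of the arthralgia row describes a reduction without a stop as follows: "reduce DFX by 50% until resolution and then escalate by 10 mg/kg/day at 1 month intervals to the former dose".

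Section 6.2 fixes a common starting dose: "For all naïve patients and patients on DFP at screening the starting DFX dose will be 20 mg/kg body weight". A 30 mg/kg start is allowed where iron is high.

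Section 9 heads its list "Reasons that a patient must discontinue participation in a clinical study", and reason 3 on that list is "DFX treatment at 10 mg/kg/day (for safety reasons) for more than 4 weeks". The section closes by counting prematurely withdrawn patients as treatment failures.

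**The concern.** A drug can be restarted only if it was stopped. The ferritin row writes no stop for DFX, yet its recovery sentence applies to every patient whose ferritin rises above 500, including those who took the halved dose throughout. Such a patient's site has to decide whether *last dose* means the dose before the reduction or the dose now being taken. Sites could give children in the same position doses that differ two-fold.

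The second issue is narrower. Halving from 20 mg/kg/day gives exactly the dose named in Section 9 reason 3. Table 4 allows that patient to continue while ferritin stays low; Section 9 lists more than 4 weeks at that dose as a reason for mandatory discontinuation. Reason 3 names DFX only. A DFX patient whose ferritin has fallen a long way could therefore be withdrawn when a DFP patient in the same position would not be.

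**Working it through.** **1. Is the wording peculiar to this row?** Table 4 has six other readable DFX restart instructions: creatinine, proteinuria, ALT/AST, skin rash, mild neutropenia and arthralgia. Each follows a written interruption. The ferritin row is the only one that does not. (The nausea/abdominal pain/vomiting row is broken in the available text and is left out.)

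**2. Dose on recovery.** Inputs: original DFX doses of 20, 30 and 40 mg/kg/day, spanning the range in Section 3.3. Reading A takes *last dose* as the pre-reduction dose: 0.5 × original. Reading B takes it as the dose being taken: 0.5 × 0.5 × original. Steps are +10 mg/kg/day per month, capped at the original dose; the cap is an assumption, since the cell gives no target.

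| Original | After halving | Recovery, A | Steps back, A | Recovery, B | Steps back, B |
|---|---|---|---|---|---|
| 20 | 10 | 10 | 1 | 5 | 2 |
| 30 | 15 | 15 | 2 | 7.5 | 3 |
| 40 | 20 | 20 | 2 | 10 | 3 |

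Under A the restart changes nothing. Under B the dose falls to a quarter of the original just as ferritin recovers.

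**3. Time at 10 mg/kg/day against the 4-week (28-day) limit**, for a patient halved from 20. Visits are monthly with a ±7-day window (Section 7.2), so a gap between two visits can move by 14 days either way.
- First check: 28–31 days; with windows 28 − 14 = 14 to 31 + 14 = 45. The limit may or may not be passed.
- Second check, if ferritin was still below 500 and DFX continued at 10: 59–62 days; with windows 59 − 14 = 45 to 62 + 14 = 76. The limit is always passed.

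Patients halved from 30 or 40 go to 15 or 20 and do not meet reason 3 through that halving.

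**4. What such a patient's ferritin shows.** With baseline ferritin above 500, a value of 500 or less meets criterion A (Section 4.3.1) at that time. Below a baseline of 2500 any decrease counts. From 2500 or more the fall is at least (2500 − 500)/2500 = 80%, against the 20% required. Patients aged 10 or over with MRI must also meet criterion B.

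**5. Effect per affected patient.**
- ITT (Section 11.6): a missing 1-year composite counts as failure. If all 194 DFX patients start therapy and this one would otherwise succeed on every applicable criterion, the DFX rate falls by 1/194 = 0.52 percentage points, or 0.52/12.5 ≈ 4% of the non-inferiority margin.
- Primary analysis (PP1, Section 11.2): it requires a composite at baseline and at 1 year, so the patient would generally drop out. As an illustration, with 155 evaluable DFX patients (310/2) and about 65% success, 101/155 = 65.2% becomes 100/154 = 64.9%, a shift of about 0.2 points.

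**The case against.** A reader might infer that the plan instructs a second halving. The documents do not support that. The cell's first sentence uses *last dose* for the dose in force when ferritin fell. The neutropenia and arthralgia rows use it for the dose before the event. Cutting to 5 mg/kg/day because ferritin has recovered would defeat the row's purpose. Permission to continue after consultation also implies that DFX might be stopped, which would give *restart* a meaning for those patients. All of this stands, and it makes reading A the more sensible one. It does not rescue the sentence: the stop is unwritten, the sentence is not confined to patients who stopped, and nothing excludes reading B.

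On Section 9, permission to continue and a time cap can be read together: continue until the cap. The section also says withdrawal may be at discretion and encourages keeping patients in where there is no medical contraindication. Reason 2, that treatment is no longer needed, applies to both arms and might cover persistent over-chelation. These points narrow the conflict and limit the asymmetry to reason 3. They do not say which rule governs a patient whom Table 4 lets continue past 4 weeks at 10 mg/kg/day.

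A reader might also infer a bias towards DFP in the primary result, since Sections 9 and 11.13 count withdrawn patients as failures. PP1 as defined generally excludes a patient with no 1-year value. The withdrawal visit takes a central ferritin, but that is not a 1-year assessment. The 0.52-point figure therefore belongs to ITT, which corroborates the primary analysis and carries the superiority test.

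**Conclusion.** The DFX recovery instruction in the ferritin row is defective as written: incoherent for patients who never stopped, silent on what *last dose* means, and without a target dose. The two readings differ by a factor of two. This is a minor point, but it concerns a dosing rule for children at many sites.

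The Section 9 conflict is real and narrow. It needs a patient halved from 20 mg/kg/day, ferritin still below 500 at the next check, and agreement to continue at 10. It holds whichever way *last dose* is read.

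Neither part supports a claim that the primary comparison is materially biased. The effect is at most 0.52 points per affected patient, in ITT only, assuming all 194 start therapy and the patient would otherwise have succeeded on all applicable criteria. The documents do not give the number of such patients; the overall effect is probably small. Annex 1, the DFX product information, appears only as a title, so its guidance could not be compared.

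**What to change.** Replace the DFX recovery sentence in the ferritin row with wording modelled on the arthralgia row, for example: *Once ferritin is above 500 ng/ml, raise DFX from the reduced dose in monthly steps of 10 mg/kg/day, up to the former dose. If DFX was stopped after consultation, resume at half the pre-reduction dose and raise it in the same way.* The clinical team should set the timing of the first step and confirm the former dose as the ceiling, since that dose preceded the low ferritin.

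The clinical team should also state which rule governs a patient kept at 10 mg/kg/day for low ferritin. One option is to exclude reductions made under this row from Section 9 reason 3. That is a clinical decision rather than a pure clarification, because it lifts the only explicit time limit on that reduced dose. If the limit is kept, the Table 4 cell should say that continuation at 10 mg/kg/day ends at 4 weeks.

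The cost is one table cell and one phrase in a protocol amendment. Sample size and analysis are unchanged.
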